This human cannabis administration research will provide the most comprehensive controlled test of how cannabis affects alcohol motivation and consumption. It may yield substantial information about the mechanisms whereby cannabis may pose a risk for the development and maintenance of problem drinking; the relative roles of these different mechanisms could inform clinical treatment and prevention efforts. The outcomes of this investigation have direct implications for public health policy as they can inform efforts to reform cannabis legislation by bridging the gap between the public's considerable misconception about perceived low risks from cannabis and lesser-known risk of increased drinking from cannabis. Characterizing cannabis's putative effects on alcohol can potentially decrease consumption by framing public health messages and via regulation of advertising and retail marketing practices in states that have or will move towards cannabis legalization.

Figure 1. Mediation Model

8. TRIAL DESIGN: Repeated measures double-blind crossover design.

Methods: Participants, interventions, and outcomes

9. STUDY SETTING: Brown University, Providence, RI, United States of America.

10. ELIGIBILITY CRITERIA: English speaking, age 21 to 44, past month cannabis use \geq twice weekly and \geq weekly in the past six months, positive urine toxicology screen for THC at baseline, smoking as a familiar mode of cannabis administration, heavy episodic drinking (≥ 5 drinks for men, ≥ 4 drinks for women per occasion) \geq once monthly over the past 12 months¹, not meeting criteria for current DSM-5 major depressive episode, manic or hypomanic episode, panic disorder, or psychotic symptoms as assessed by the SCID, ability to abstain from alcohol and cannabis for 24 hours without withdrawal (Clinical Institute Withdrawal Assessment for Alcohol, revised-CIWA-AR score < 8 at each experimental visit), no intent to quit or receive treatment for cannabis or alcohol use disorder, negative pregnancy test and not nursing, negative urine toxicology screen for drugs other than cannabis, no contraindicated medical issues and body mass index ≤ 30 and weighing < 250 lbs confirmed via physical exam, no history of seizures; ≤ 20 tobacco cigarettes daily for tobacco smokers; history of simultaneous alcohol and cannabis use on the same occasion.

10a. ELIGIBILITY CRITERIA selection:

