¹ Eligibility criteria for heavy episodic drinking changed from twice per month to once per month on 10/27/2017 after 15% of the sample was recruited.

The lower limit of the 21-44 age range was selected due to the ethical and legal restrictions and risks of alcohol administration to younger individuals. Younger individuals (< 30 years of age) and middle-age individuals (between 31 and 50) have the highest rates of cannabis and alcohol use (SAMHSA, 2019). Cardiovascular risk (e.g., myocardial infarction/fatal coronary heart disease) (Vassale et al., 2009; Stramba-Badiale et al., 2006; Dhingra & Vasan, 2012; Barnett et al., 2006; Mozaffarian et al., 2015) significantly increases in middle age (i.e., after the age of 40), and cardiovascular risk is of particular concern due to the well-established acute effects of cannabis involving ventricular tachycardia and increased risk of myocardial infarction in individuals with underlying cardiovascular disease (Goyal et al., 2017). Further, there are notable differences in liver function (Cieslak et al., 2016; Meier et al., 2008), body composition (i.e., decreased lean muscle, mass, decreased volume of body water) (St-Onge & Gallagher, 2010), and resting metabolic rates (Krems et al., 2005) that alter the body's ability to process alcohol in later middle age. Thus, the cutoff age of 44 was conservatively selected to minimize health risks and to ensure findings on alcohol-related outcomes would not be confounded by age-related changes.

History of simultaneous alcohol and cannabis use is assessed at study screening with the following question, "*Have you ever used marijuana and drank alcohol on the same occasion?*" This criterion was included for ethical and for safety reasons to ensure participants have prior experience of using cannabis and alcohol on the same occasion. It also ensures findings are generalizable to all individuals who co-use cannabis and alcohol.

11a. INTERVENTIONS: Three experimental double-blind sessions in which participants smoke 1 cannabis cigarette with 7.2% THC, 1 cannabis cigarette with 3.1% THC, and 1 cannabis placebo cigarette, with the order of administration counterbalanced across subjects.

11b. Discontinuing the administration of cannabis and alcohol in an experimental session

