16a. SEQUENCE GENERATION: Randomization to the cannabis dose order for the three available doses (i.e., 7.2%, 3.1%, and 0% THC) occurs before the first experimental session. The six predefined order permutations are: (1, 2, 3), (1, 3, 2), (2, 1, 3), (2, 3, 1), (3, 1, 2), and (3, 2, 1). For randomization to one of the six orders, each participant is assigned to the next available order in the sequence. Once all orders are filled, the assignment continues from the beginning of the list, ensuring all orders are used in a balanced manner.

16b. ALLOCATION CONCEALMENT MECHANISM: In order to maintain double-blind conditions (participants and research assistants), cannabis cigarettes are prepared by the PI or Co-I who randomizes participants to the cannabis dose conditions but who has no contact with study participants.

16c. IMPLEMENTATION: The PI or Co-I assigns participants sequentially to the next available drug dose order.

17a. BLINDING: Research assistants and participants remain blinded to the cannabis dose order assignment.

17b. Unblinding may be permissible if necessary in the event that an individual participant were to be discontinued from the study if their safety were at risk (e.g., adverse reaction to cannabis or alcohol for which further participation in the study is no longer safe).

18. Methods: Data collection, management, and analysis

18a. DATA COLLECTION METHODS:

The following sections describe protocol procedures from the start of study recruitment in February 2017 through March 16, 2020 when research operations were ceased due to the mandatory COVID-19 pandemic laboratory closure. The study was permitted to resume laboratory research operations in July 2020 under a modified protocol due to COVID-19 precautions and was completed in May 2021. As a result of the COVID-19 pandemic, some of the in-person research procedures were suspended. Specifically, the modified study protocol did not include blood collection or computer-based tasks during the experimental sessions. Study screening procedures were also designed to minimize in-person contact [see COVID-19 Modifications to Protocol below].

Design Overview. This project uses a within-subjects repeated measures experimental design to examine the effect of 7.2% THC and 3.1% THC dose of cannabis, relative to placebo, on alcohol craving, cue-induced incentive salience, and subsequent drinking in an alcohol choice task in which participants choose either to

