20a. STATISTICAL METHODS: The dose-dependent effect of THC on alcohol DVs: (1) post-smoking urge to drink alcohol and cue-induced alcohol craving on the ACQ, and (2) amount of alcohol consumed on the Alcohol Choice Task will be tested using repeated measures mixed model analyses. The first step in the model tests Aim 1 (the primary outcome of the grant) and includes 1) static covariates (session order number), 2) session-varying (cannabis vs placebo dose) value of the respective DV assessed before smoking or after neutral cue (craving); 3) and dummy-coded cannabis condition with placebo as the reference group. Analysis of the percent alcohol consumed will mirror the above analytic approach.

20b. Methods for Plasma THC Concentrations Analysis

All participants included in the blood data analysis had data from the pre-smoking and immediate post-smoking timepoints, with some blood draws not done for 2 to 6 participants across the other three post-smoking timepoints. Blood samples collected post-smoking in the placebo condition were assayed for the first 25 participants because THC levels remain stable in this condition over several hours. To analyze cases where the post-smoking placebo values were not available, post-smoking cannabinoid levels in the two active THC conditions were compared to the pre-smoking placebo levels, covarying for the pre-smoking value of the respective active THC dose.

Methods: Monitoring

21a. DATA MONITORING: The following data and safety monitoring plan will be implemented for the protection of research participants and data. The study coordinator will monitor protocol adherence and will report to the PI. This individual will assess adherence via direct observation of the study visits, visual inspection of the completeness of data collection, verification procedures for the scanned scantrons of the case report forms, and all participant communication outside of study visits. Weekly reporting procedures are in place for routine operations and immediate/daily communication will take place depending on the time sensitive nature of communication. The PI will be informed immediately of any adverse event.

21b. N/A

22. HARMS:

Potential Risks to Subjects.

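### The Aim 1 crossover model lists session order as a static covariate and names no categorical session (period) factor, so the dose tests may be conservative

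*Combined protocol and SAP*

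**What the plan says.** Section 8 describes the trial as a "Repeated measures double-blind crossover design". Section 11a has three sessions, one per dose, "with the order of administration counterbalanced across subjects". Section 16a lists the orders: "The six predefined order permutations are: (1, 2, 3), (1, 3, 2), (2, 1, 3), (2, 3, 1), (3, 1, 2), and (3, 2, 1"). Participants take the next order on the list in rotation.

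Section 20a says that the dose effects "will be tested using repeated measures mixed model analyses". The first step, which tests Aim 1, has three parts:

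- It "includes 1) static covariates (session order number").
- It has a "session-varying (cannabis vs placebo dose) value of the respective DV assessed before smoking or after neutral cue (craving").
- It has "dummy-coded cannabis condition with placebo as the reference group".

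For drinking, "Analysis of the percent alcohol consumed will mirror the above analytic approach". Section 20a does not say how session order number is coded, and it names no categorical session factor.

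**The concern.** In a three-session crossover, responses may change with repetition whatever the dose: participants may habituate to the cues, find the bar laboratory less novel, or learn the drink-or-money task. A model normally carries a session (period) term so that this change does not sit in the within-person residual against which dose is tested.

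The plan sets *static* against *session-varying*. A static quantity is constant within a participant, which points to the assigned order, one of the six permutations. Such a term explains differences between participants and nothing that happens from session to session. If the session's own number (1, 2, 3) was meant, *static* is the wrong word, and a single numeric term removes only straight-line change. At stake are the size of the standard errors and the power of both dose contrasts, for craving and for percent alcohol consumed.

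**Working it through.** **Inputs.** From the documents: three sessions, six orders used equally (16a), and N = 120, two-tailed alpha .017 and power .80 (14). Section 14 also states alpha .01, so that value is checked below. The plan gives no period effect and no standard error for a dose contrast, so it has no figure of its own to reproduce on this point. N = 120 serves only as a benchmark; how it was derived is a separate matter. The size of the period effect is an assumption, in within-person SDs (σ_w = 1).

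**Step 1: error variance.** With each dose equally often in each session, leaving session effects p1, p2, p3 out of the model multiplies the estimated within-person error variance by about

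F = 1 + Σ(p_j − p̄)² / (2σ_w²).

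- Linear drift d per session: the deviations are −d, 0, d and the sum is 2d², so F = 1 + d².
- Shift s in the first session only: the deviations are 2s/3, −s/3, −s/3 and the sum is 2s²/3, so F = 1 + s²/3.
- The same shift with a linear session term in the model: the linear part of the sum is s²/2, which leaves 2s²/3 − s²/2 = s²/6, so F = 1 + s²/12.

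**Step 2: power.** Balance leaves the sampling distribution of the dose estimate unchanged; only the estimated standard error grows, by √F. With the dose effect set to give power .80 under a categorical session factor (normal approximation),

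power = Φ(z.9915 + z.80 − z.9915·√F) = Φ(3.228 − 2.387·√F).

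| Term in the model | Assumed period effect | F | Power |
|---|---|---|---|
| Assigned order (static) | drift 0.1 per session | 1.01 | .80 |
| Assigned order (static) | drift 0.3 per session | 1.09 | .77 |
| Assigned order (static) | drift 0.5 per session | 1.25 | .71 |
| Assigned order (static) | first session 0.5 | 1.08 | .77 |
| Assigned order (static) | first session 1.0 | 1.33 | .68 |
| Session 1–3, linear | any linear drift | 1.00 | .80 |
| Session 1–3, linear | first session 0.5 | 1.02 | .79 |
| Session 1–3, linear | first session 1.0 | 1.08 | .77 |
| Session, three levels | any shape | 1.00 | .80 |

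Worked row: for d = 0.5, √1.25 = 1.118 and 3.228 − 2.387 × 1.118 = 0.560, so Φ = .71. At alpha .01 the constants are 3.417 and 2.576, and drifts of 0.1, 0.3 and 0.5 give power .796, .767 and .705, so the choice of alpha hardly matters here.

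**Step 3: simulation** (N = 120, 2,500 runs per scenario, alpha .017, drift 0.5 per session, no baseline covariate).

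| Model | Mean model SE | Empirical SE | Power | Type I error |
|---|---|---|---|---|
| Assigned order | .144 | .130 | .72 | .006 |
| Session, linear | .129 | .130 | .81 | .018 |
| Session, three levels | .129 | .130 | .81 | .018 |

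The mean estimate was the same in all three models (.424 for a true .423).

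**Step 4: the baseline covariate.** When the pre-smoking value was simulated to share the drift, with an assumed coefficient of .5, power under the assigned-order model was .79 instead of .72. Section 20a includes such a value for craving. For percent alcohol consumed no pre-smoking value is described, so there session order is the only non-dose term that could take up session effects.

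**The case against.** The strongest reply is that everything turns on one adjective. Section 16a calls the assigned sequence a dose order or an order permutation, never a session order number. That phrase reads at least as naturally as the ordinal number of the session, with *static* a loose label for a design covariate. On that reading linear drift is fully removed, and even a first-session shift of 1.0 SD leaves only 8% in the error variance. This stands: it cannot be said as fact that session-to-session change is left in the error of every dose contrast. What remains is that the text does not settle the reading, and that neither reading gives a categorical session factor.

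Three stronger inferences are tempting, and the material does not support them.

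- *The dose contrasts are biased.* With six orders in equal use and complete data they are not. Loss linked to dose could disturb that balance, since section 11b removes participants who do not finish the cigarette, but no material bias has been shown.
- *The dose estimates are noisier, or 120 participants yield the information of fewer.* The empirical SE was the same in all three models. Only the reported SE is too large, so the error is towards caution and there is no added false-positive risk.
- *The full loss applies to craving.* The session-varying baseline takes up part of any drift it shares with the outcome.

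It is also fair to say that a six-level order factor is not needed to remove period effects.

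**Conclusion.** The concern holds in a limited form. The Aim 1 model names no categorical session factor, and the one session-related term is either a participant-level code that cannot absorb session effects or a mislabelled session number whose coding is unstated.

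Under the literal reading, and without help from a baseline covariate, the cost is conservative tests: negligible at 0.1 SD per session, about 3 points of power at 0.3, and about 9 at 0.5. Under the linear reading it is zero for linear drift and about 1 to 3 points for a first-session shift of 0.5 to 1.0 SD. All of these figures rest on assumed period effects, complete balance over the six orders, and the N = 120, alpha .017 benchmark. The concern weighs most for percent alcohol consumed and less for craving.

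**What to change.** In section 20a, replace the static session order covariate with: session (1, 2, 3) as a three-level categorical within-participant factor. State that this applies to both the craving and the percent-alcohol models. Assigned order may be added as a categorical between-person factor, but this is optional.

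The cost is a line of text and code and two within-person degrees of freedom, out of 120 × (3 − 1) = 240 for 120 completers. If there is no period effect, almost nothing is lost: in simulation without one, power was .81 with all three codings. The change also settles how the term is coded.

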14. SAMPLE SIZE: A sample size of 120 is required to test Primary Aim 1: cannabis's acute effects on incentive salience of alcohol after exposure to alcohol cues and on alcohol consumption, as indexed by subjective craving for alcohol and alcohol consumption (percent of total available alcohol consumed on an alcohol choice self-administration task).

Power estimates and sample size calculations were conducted with a two-tailed $\alpha = .017$ and power of at least .80 (Cohen, 1988). Effect size estimate was informed by our preliminary results and the literature (Ballard & de

Wit, 2011; Lukas & Orozco, 2001; [name] et al., 2011, 2012), which indicated a large effect of cannabis administration (3.0%THC) on positive subjective effects ($d = 2.45$), a moderate effect on negative emotional processing ($d = .56$), a small ($sr^2 = .03$) effect on disinhibition; a small effect ($d = .12$) of cannabis cue reactivity on alcohol craving. The effect size of low dose of THC combined with low dose of alcohol on self-report of “wanting more drug” was found to be large, $r^2 = .48$ (Ballard & de Wit, 2011). The effect size for a low dose of alcohol pretreatment combined with moderate dose cannabis on the number $r^2 = .47$ and duration $r^2 = .63$ of euphoric events was found to be large (Lukas & Orozco, 2001). The above referenced literature demonstrates highly relevant effect size estimates, although there is no one study that has tested directly the hypotheses in this application. Thus, we assumed conservatively that the effect of cannabis administration on alcohol craving and consumption will be at least of medium magnitude, accounting for at least 5% of the variance in a given alcohol DV. With power of .80 and alpha at .01, a sample size of 120 would be required to detect an effect of cannabis dose when tested in conjunction with the relevant covariates.

15. RECRUITMENT: Participants are recruited through advertisements in newspapers, on Craig’s list, through community bulletin boards including digital university-specific newsletters, and community-based events. Responders to study advertisements are asked to complete an initial brief screen using online survey software. If eligible, they are then screened by phone), followed by more rigorous screening at baseline for inclusion criteria.

16. Methods: Assignment of interventions (for controlled trials)

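### Section 20a enters pre-smoking craving as one session-varying covariate, so its slope can blend between-person and within-person association and cost the dose contrasts some precision; splitting it in two is a near-free remedy

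*Combined protocol and SAP*

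**What the plan says.** Section 8 describes a "Repeated measures double-blind crossover design". Under section 16a there are six dose orders, and "each participant is assigned to the next available order in the sequence", so orders are balanced and each dose contrast is made within participants.

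Section 20a says that the alcohol outcomes "will be tested using repeated measures mixed model analyses". For Aim 1 it lists three kinds of term: session order, the "session-varying (cannabis vs placebo dose) value of the respective DV assessed before smoking", and "dummy-coded cannabis condition with placebo as the reference group". The baseline term has two candidates: "value of the respective DV assessed before smoking or after neutral cue (craving"). It appears once, without a participant-mean term or centring. Random effects and covariance structure are not given.

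Section 12 places T0 before smoking and the post-neutral-cue assessment (T2) at 47 minutes, after smoking. Section 14 concludes that "a sample size of 120 would be required to detect an effect of cannabis dose when tested in conjunction with the relevant covariates". It gives no within-person SD, between-session correlation or baseline-outcome slope.

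**The concern.** Write the model as Y = session order + g·X + dose terms + person effect + error, with X the T0 value at that session. The dose contrasts compare a person with himself or herself. The baseline helps only so far as a session with unusually high T0 craving for that person is also followed by unusually high craving later. That is the within-person slope.

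One coefficient on uncentred X also draws on the between-person relation: people who generally crave more score higher at every time point. If that relation is steeper, g is pulled above the within-person slope, and chance differences in T0 between a person's sessions are over-corrected. The over-correction averages to zero across balanced orders, so it adds noise and not bias. At stake is some power for the craving contrasts that the collected data could supply. Percent of alcohol consumed has no pre-smoking value, so the point concerns craving.

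**Working it through.** **The plan's own figure.** Section 14 gives N = 120 for 5% of variance at power .80, and states alpha both as .017 and as .01. Treated as an R² increment with f² = .05/.95 = .0526, alpha .01 and 1 df, N is 226, and power at 120 is .46. A figure near 120 appears only with an unstated share explained by covariates: total R² = .50 gives f² = .05/.50 = .10 and N = 121. This does not show 120 to be wrong. It shows that the figure depends on covariates whose contribution is not given.

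**Assumptions for the check.** N = 120, three sessions, six balanced orders, random intercept, two-sided alpha .017, and X and Y with unit variance. Let ρ be the between-session correlation, b the between-person and w the within-person baseline-outcome correlation. All three are assumed.

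**Pooled slope at ρ = .7, b = .95, w = .30.**
- Variance of a person mean: m = ρ + (1−ρ)/3 = .80.
- Covariance of person means: c = ρb + (1−ρ)w/3 = .665 + .030 = .695. Slope on the means: .695/.80 = .869.
- Residual variances at slope g: within, s_w = (1−ρ)(1 − 2gw + g²); means, s_m = m(1+g²) − 2gc.
- Weights: A = 2(1−ρ)/s_w and B = m/s_m. The slope solves g = (A·w + B·.869)/(A + B).
- At g = .668: s_w = .314, s_m = .229, A = 1.91, B = 3.50, and (.573 + 3.04)/5.41 = .668.

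The pooled slope is therefore about .67 against a within-person slope of .30.

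**Cost in that setting.** Variance inflation of a dose contrast is 1 + (g−w)²/(1−w²) = 1 + .37²/.91 = 1.15, so 120 participants act like 120/1.15 = 104. Set the effect for .80 power with the split covariate (2.387 + .842 = 3.229). The pooled slope gives 3.229/√1.15 − 2.387 = .624, power .73. No baseline gives 3.229·√.91 − 2.387 = .693, power .76.

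**When the planned adjustment does worse than none.** Its variance is proportional to 1 − 2gw + g², against 1 without a baseline, so it is worse only when g > 2w.

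**Simulation** (random-intercept REML, 1,500 trials per row; g from the formula above):

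| ρ / b / w | g | 2w | Pooled | Split | None | Loss, points |
|---|---|---|---|---|---|---|
| .5 / .95 / .3 | .56 | .6 | .775 | .809 | .769 | 3.4 |
| .7 / .95 / .3 | .67 | .6 | .729 | .792 | .751 | 6.3 |
| .7 / .90 / .1 | .49 | .2 | .741 | .806 | .806 | 6.5 |
| .7 / .90 / .5 | .70 | 1.0 | .789 | .805 | .687 | 1.6 |
| .8 / .95 / .1 | .65 | .2 | .660 | .779 | .773 | 11.9 |
| .8 / .90 / .5 | .72 | 1.0 | .776 | .802 | .670 | 2.6 |

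The pooled model falls below no baseline exactly in the rows where g exceeds 2w.

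**Wider ranges** (ρ = .5 and .7, 1,000 trials per cell):
- b .60-.75 with w .5-.8: loss about 1 point or less.
- b .60-.75 with w .3: 0-2 points.
- b .90 with w .6-.8: 0-2 points.
- b .95 with w .6-.8: about 1-3 points.

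**Set up by slopes instead** (between/within, N = 120, alpha .01): .8/.8 and .8/.6, no visible loss; .8/.4, 1-2 points; .8/.2, 2-5; 1.0/.2, 3-8; 1.0/0, 2-11. At 1.0/0 with N = 120-150 and alpha .017, or N = 150 and alpha .01, the loss was 9-13 points.

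**Validity.** Dose estimates were unbiased throughout, and type I error was .046-.052 at nominal .05.

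**The case against.** The strongest reply is that one session-varying baseline is a conventional and valid choice, and that the large losses sit in a corner of the assumptions. T0 and the first post-smoking rating use the same questionnaire, separated by little more than a 10-minute smoke, so the within-session correlation may well be high. Where it is .5 or more, the planned covariate recovers most of the available gain and clearly beats no baseline (for example .789 against .687 above). This stands, and it is why the size is given as a range that starts at zero.

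Second, the background section targets 150 participants. With inflation of 1.15, 150 act like 150/1.15 = 130, still above 120. That is true, but headroom is no reason to give up precision that costs nothing.

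Third, the person effect and the uncentred entry are inferred from what section 20a lists. With fixed person effects the slope would already be purely within-person and the point would fall away. The point therefore holds for the usual random-intercept reading.

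A reader might also infer that the dose contrasts are biased, that the false-positive rate is wrong, or that baseline adjustment should be dropped. Neither the documents nor the calculations support these for the pre-smoking covariate.

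**Conclusion.** The mechanism holds under a random-intercept reading of section 20a, and it concerns precision only. No correlation or slope is documented, so the size is conditional. At N = 120 the loss is:
- about 0-2 points of power if the two slopes are similar, or if the within-session correlation is .5 or more with a moderate between-person correlation;
- about 1-5 points for moderate differences;
- about 10-13 points only if craving is very trait-like and the within-session slope is near zero. The worked example, at about 6 points, lies between.

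The planned adjustment can do no better than no baseline only where the within-person slope is low, about .3 or less, and the between-person relation is steep. It would be too strong to say that the primary contrasts lose power as a matter of course, or that the trial is underpowered for this reason.

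The point does not extend to the post-neutral-cue covariate. That value is taken after smoking, so adjusting for it can absorb part of the dose effect (an assumed shift of .2 with slope .5 removes .2 × .5 = .10). Splitting it into mean and deviation does not prevent this.

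**What to change.** In section 20a, replace the single pre-smoking covariate with two terms built from the same T0 data: (a) the participant's mean T0 value across sessions and (b) that session's T0 value minus that mean. Keep the dose terms and the person effect, and state the random effects and covariance structure so that the model is unambiguous. Limit the split to baselines measured before dosing, and treat the post-neutral-cue covariate as a separate question.

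The cost is one sentence and one degree of freedom. Craving is already collected before smoking at every session, so no new data are needed. If the two slopes prove equal, that degree of freedom is the only loss. Section 18a says that the study was completed in May 2021. If the primary analysis is already fixed, report the split model as a labelled sensitivity analysis.
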